5.1 Inclusion Criteria

In order to be eligible to participate in this study, an individual must meet all of the following criteria:

1. Provision of signed and dated informed consent form.
2. Able to understand and willing to be available for all study visits and comply with all study procedures including Lifestyle Considerations (see [Section 5.4](#)) throughout the study.
3. Male and Female individuals, age 18-65 inclusive at time of enrollment.

4. Good general health by medical history (MH), physical examination (PE), and vital signs (VS), clinical laboratory tests and ECG within normal reference range.¹
 - Note 1: Lab exceptions include: lab test values that are within Grade 1 range per the Toxicity Table ([Appendix A](#)) are acceptable if not considered to be clinically significant by the investigator (PI, sub-investigator, or authorized clinician), with the exception of liver function tests (LFT) (transaminases ALT, AST, alkaline phosphatase (AP), total and direct bilirubin, serum creatinine, estimated glomerular filtration rate (eGFR) per the CKD-EPI formula, and urine protein, which must be within the laboratory normal reference range.
 - Note 2: Screening laboratory values that fall outside the laboratory normal reference ranges and the ranges are not listed within the Toxicity Table ([Appendix A](#)) (e.g., decrease aPTT) that are deemed Not Clinically Significant by the PI will be acceptable.
5. Ability to take oral medication and be willing to adhere to the dosing regimen.
6. Women of childbearing potential¹ must have practiced or use true abstinence² or use at least one acceptable primary form of contraception³ for specified periods⁴ before, during and after dosing.
 - Note 1: Not of childbearing potential – post-menopausal females (defined as having a history of amenorrhea for at least one year) or a documented status as being surgically sterile (hysterectomy, bilateral oophorectomy, salpingectomy, tubal ligation, or Essure[®] placement with a history of documented radiological confirmation test at least 90 days after the procedure).
 - Note 2: True abstinence is 100% of the time without sexual intercourse (the male's penis enters the female's vagina). Periodic abstinence [e.g., calendar, ovulation, symptothermal, post-ovulation methods] and withdrawal are not acceptable methods of contraception.

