## 9. SAFETY EVALUATION

All safety analyses will be performed using the Safety Population and will be presented by Treatment Group. TEAEs will be presented in listings and summarized. Individual results of laboratory tests, VS, and ECGs will be listed and baseline, post dose, and changes from baseline to post dose laboratory, VS, and ECG data will be summarized.

In general, TEAEs, including abnormal laboratory values, will be graded according to the FDA Guidance: Toxicity Grading Scale for Healthy Adult and Adolescent Volunteers Enrolled in Preventive Vaccine Clinical Trials (<https://www.fda.gov/media/73679/download>). Grading scales are provided for AEs (**Table 6**), supine vital signs (**Table 7**), clinical laboratory results (**Table 8**), and ECG results (**Table 9**). Abnormal PE findings will be presented in data listings (**Listing 18**).

Clinical laboratory tests and VS at Screening Visit and Check-in (Day -1) should be within site normal reference range with exceptions as allowed per **Section 4.3.1**, inclusion criterion #4 and outlined in the Manual of Procedures (MOP). Grade 1 measurements acceptable at baseline will only be considered a TEAE post-baseline if condition worsened.

All TEAEs will be summarized using frequency counts and percentages. The following summaries will be presented for TEAEs and SAEs:

- Overall (i.e., regardless of severity or relationship to treatment).
- By severity grade (mild, moderate, severe, or life-threatening).
- By relationship to study drug.
- By MedDRA level hierarchy (system organ class [SOC], higher level group term [HLGT], and preferred term [PT]).

Unless otherwise specified, at each level of participant summarization in reporting the incidence of TEAEs, a participant will be counted once if the participant reported one or more TEAEs. If more than one occurrence of a TEAE is reported, the TEAE of the worst severity or the worst-case relationship assessment will be summarized.

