### 14.3.5 Displays of Laboratory Results

#### 14.3.5.1 Chemistry Results

##### Table 33: Chemistry Laboratory Results by Parameter, Maximum Severity, Time Point, and Treatment Group, Safety Population

[Implementation Note: Chemistry results will be presented for Check-In (Day -1)(baseline), 2, 4, 6, and 8 and for each treatment group.

If there are no life-threatening/grade 4 chemistry results reported, then the rows will be omitted. If there is not at least one graded event for a treatment group within a parameter, then only “None” row will be shown. If there are more than one graded event within a parameter for a specified time point, then report the maximum severity.

If the grade is zero counts, then populate the cell with “-”.

Parameters will be shown in the following order: Any Chemistry Parameter, Sodium, Potassium, Total Carbon Dioxide, Calcium, Creatinine, Blood Urea Nitrogen, Fasting Glucose, Total Protein, Albumin, Total Bilirubin, Alanine Aminotransferase, Aspartate Aminotransferase, Alkaline Phosphatase, Amylase, Lipase, Magnesium, and Inorganic Phosphorus.

Parameters will specify increase or decrease. If a parameter can both increase and decrease, then the parameter decrease will be listed first.

The following parameters may decrease: Sodium, Potassium, Total Carbon Dioxide, Calcium, Total Protein, Albumin, Magnesium, and Inorganic Phosphorus.

The following parameters may increase: Sodium, Potassium, Total Carbon Dioxide, Calcium, Creatinine, Blood Urea Nitrogen, Fasting Glucose, Total Bilirubin, Alanine Aminotransferase, Aspartate Aminotransferase, Alkaline Phosphatase, Amylase, and Lipase.]

Severity	Treatment Group	Day -1 (Baseline)		Day 2		Day 4		Day 6		Day 8		Any Time Post Baseline	
		n/N	%	n/N	%	n/N	%	n/N	%	n/N	%	n/N	%
Any Chemistry Parameter													
None	400 mg SLV213	x/x	xx	x/x	xx	x/x	xx	x/x	xx	x/x	xx	x/x	xx
	Placebo												
	All Participants												
Mild	400 mg SLV213												
...	...												

**Table 33: Chemistry Laboratory Results by Parameter, Maximum Severity, Time Point, and Treatment Group, Safety Population (continued)**

Severity	Treatment Group	Day -1 (Baseline)		Day 2		Day 4		Day 6		Day 8		Any Time Post Baseline	
		n/N	%	n/N	%	n/N	%	n/N	%	n/N	%	n/N	%
Moderate	400 mg SLV213												
	...												
Severe	400 mg SLV213												
	...												
Life-Threatening	400 mg SLV213	X	XX	X	XX	X	XX	X	XX	X	XX	X	XX
	...												
Sodium, Decrease													

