None	400 mg SLV213												
...	...												
Mild	400 mg SLV213												
	...												
Moderate	400 mg SLV213	X	XX	X	XX	X	XX	X	XX	X	XX	X	XX
	...												
Severe	400 mg SLV213												
	...												
Life-Threatening	400 mg SLV213												
	...												

**Table 33: Chemistry Laboratory Results by Parameter, Maximum Severity, Time Point, and Treatment Group, Safety Population (continued)**

Severity	Treatment Group	Day -1 (Baseline)		Day 2		Day 4		Day 6		Day 8		Any Time Post Baseline	
		n/N	%	n/N	%	n/N	%	n/N	%	n/N	%	n/N	%
Sodium, Increase													
None	400 mg SLV213												
...	...												
[Repeat for each chemistry parameter]													
Note: The “Any Time Post Baseline” column indicates the maximum severity experienced by each participant at any time point post baseline, including unscheduled assessments. Abnormal laboratory events were only considered an adverse event if the graded severity worsened from baseline.													
N = Number of participants in the Safety Population with the laboratory result assessed at the respective time point; n = Number of participants with the maximum grade experienced for the specified parameter and time point.													

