		...											
Max Severity Post Baseline	Any Time	400 mg SLV213											
		...											
Oral Temperature													
Day 1	Pre-Morning (Baseline)	400 mg SLV213		x	x	xx	x	xx	x	xx	x	xx	x
	...	...											
Day 9	N/A	400 mg SLV213											
		...											

**Table 37: Supine Vital Signs by Assessment, Maximum Severity, Time Point, and Treatment Group, Safety Population (continued)**

Time Point	Dose	Treatment Group	N	None		Mild/ Grade 1		Moderate/ Grade 2		Severe/ Grade 3		Life-Threatening/ Grade 4	
				n	%	n	%	n	%	n	%	n	%
Max Severity Post Baseline	Any Time	400 mg SLV213											
		...											
Systolic Blood Pressure, Low													
Day 1	Pre-Morning (Baseline)	400 mg SLV213	x	x	xx	x	xx	x	xx	x	xx	x	xx
	...	...											
Day 9	N/A	400 mg SLV213											
		...											
Max Severity Post Baseline	Any Time	400 mg SLV213											
		...											
[Repeat for all vital sign assessments]													
Note: The “Max Severity Post Baseline” rows indicate the maximum severity experienced by each participant at any time point post baseline, including unscheduled assessments.													
N = Number of participants in the Safety Population with the laboratory result assessed at the respective time point; n = Number of participants with the maximum grade experienced for the specified assessment and time point.													
Vital signs were collected prior to and after each dose (morning and evening) on Days 1 through Day 9 and collected in the morning during follow-up visits (Day 8 and Day 9).													

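### Tables 33–37 grade post-dose laboratory and supine vital-sign results without reference to the participant's baseline grade, so stable Grade 1 values recur as Mild and no by-arm graded-result table shows who worsened.

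*SAP*

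**What the plan says.** **What the tables count.** In SAP Table 33, the Any Time Post Baseline "column indicates the maximum severity experienced by each participant at any time point post baseline, including unscheduled assessments". The cell count is defined as "n = Number of participants with the maximum grade experienced for the specified parameter and time point", with no condition on the baseline grade. Tables 34–36 are specified as similar in format to Table 33. In Table 37, the Max Severity Post Baseline "rows indicate the maximum severity experienced by each participant at any time point post baseline, including unscheduled assessments".

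**What may be present at entry.** Protocol 5.1, criterion 4, Note 1 allows "lab test values that are within Grade 1 range per the Toxicity Table" if the investigator judges them not clinically significant. It excepts ALT, AST, alkaline phosphatase, total and direct bilirubin, creatinine, eGFR and urine protein, which must be normal. SAP 9.7 treats Grade 1 supine vital signs at entry in the same way.

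**How the adverse-event analysis treats them.** SAP 9 states: "Grade 1 measurements acceptable at baseline will only be considered a TEAE post-baseline if condition worsened". SAP 9.6 and 9.7 repeat the rule. The Table 33 note adds: "Abnormal laboratory events were only considered an adverse event if the graded severity worsened from baseline". The Table 37 note has no such sentence.

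**What baseline information is shown.** For Table 33, "Chemistry results will be presented for Check-In (Day -1)(baseline), 2, 4, 6, and 8 and for each treatment group". Table 37 has a Day 1 pre-dose baseline row by arm.

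**The concern.** The SAP uses two rules for the same measurement. A stable entry Grade 1 is not treatment-emergent, yet Tables 33–37 print it as Mild on each day it is observed, in the post-baseline maximum, and in the Any parameter rows. On the SAP's own scales this is easy to meet: fasting glucose of 100–110 mg/dL is Grade 1 in Table 8.

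The baseline column or row gives the arm's distribution, not each participant's path. A reader who sees Mild before and after dosing cannot tell carried-over grades from new ones. With arms this small, one or two participants move a percentage a long way. Old grades can then dilute a real difference between the arms or imitate one. SAP 9 says changes from baseline in laboratory and vital-sign data will be summarized, but none of the shells for Tables 33–37 gives a numeric change or a grade shift. Table 38 shifts only the overall ECG interpretation.

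**Working it through.** **Inputs**
- Planned size: SAP 5 gives 12 per cohort, 8 active and 4 placebo. Over three cohorts, 3 × (8 + 4) = 36, which reproduces the stated total. (SAP Table 4 shows 6, 6, 6 and 18. That also sums to 36 but conflicts with 8 + 4 per cohort and needs separate reconciliation; 8:4 is used here.)
- Only Cohort 1 was enrolled. SAP 6.2 records four replacements, and SAP 6.3.3 includes replacements in the Safety Population, so it may reach 12 + 4 = 16. The arms of the replacements are not stated.
- Prevalence p of a stable Grade 1 at entry, for a given table row: not in the documents. Assumed 10–40%, equal in both arms, persisting after dosing, with no drug effect.

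**What the arm totals can and cannot show.** Suppose 2 of 8 active participants are Mild for glucose at baseline and 2 of 8 are Mild post-baseline. If they are the same two people, nobody worsened. If they are different people, two worsened and two resolved. Table 33 prints the same figures either way, so the number who worsened could be 0, 1 or 2.

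**Chance imbalance, fixed number of carriers.** If 2 of 12 carry a stable Grade 1, both fall on active with probability C(8,2)/C(12,2) = 28/66 = 0.42. The table then shows Mild in 2/8 (25%) against 0/4 (0%). A worsened-from-baseline count shows 0/8 against 0/4.

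**Chance imbalance, assumed prevalence.** With a ~ Bin(n₁, p) on active and b ~ Bin(n₂, p) on placebo, compute P(|a/n₁ − b/n₂| ≥ 0.25).

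Step for 8:4 and p = 0.10. The complement is |a − 2b| ≤ 1:
- b = 0, a = 0 or 1: 0.6561 × (0.4305 + 0.3826) = 0.5335
- b = 1, a = 1 to 3: 0.2916 × (0.3826 + 0.1488 + 0.0331) = 0.1646
- b = 2, a = 3 to 5: 0.0486 × (0.0331 + 0.0046 + 0.0004) = 0.0019
- b ≥ 3: negligible

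The sum is 0.700, so the probability is 0.300.

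| Active:placebo | p = 0.10 | p = 0.20 | p = 0.30 | p = 0.40 |
|---|---|---|---|---|
| 8:4 (planned) | 0.300 | 0.445 | 0.511 | 0.541 |
| 12:4 | 0.206 | 0.366 | 0.445 | 0.473 |
| 11:5 | 0.113 | 0.262 | 0.333 | 0.358 |
| 10:6 | 0.087 | 0.197 | 0.275 | 0.333 |
| 8:8 | 0.192 | 0.339 | 0.411 | 0.444 |

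The last four rows are the 16-participant splits tried (4, 3, 2 or 0 replacements on active).

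These probabilities cover both directions. An excess on active of 25 points or more at 8:4 has probability 0.124, 0.227, 0.262 and 0.273. Under a worsened-from-baseline count, every stable carrier contributes zero in both arms.

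**The case against.** Much can be said for the plan.

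- **A reader might infer that entry Grade 1 values are reported as toxicity.** The documents do not support that. These shells display graded results, the Table 33 note itself limits adverse events to worsened grades, and Table 14 counts only Grade 3.
- **A reader might infer that no by-arm display allows for baseline.** That is also too strong. The notes to Tables 22 and 23 include laboratory events as adverse events, and Tables 22–25 present events by arm under the worsening rule. They do not fully fill the gap: Tables 23–25 are arranged by MedDRA term rather than by parameter and direction, and Protocol 8.5.6 records a laboratory abnormality that belongs to a syndrome under the syndrome.
- **A reader might infer that the imbalance is hidden or individuals cannot be traced.** Baseline grades are printed by arm beside the post-dose ones. Tables 29–32 list abnormal results by participant, Listings 13–16 give every laboratory result and Listing 17 every vital sign. With about 16 participants, tracing is feasible, but it is left to the reader.
- **The organ of most interest is protected.** Protocol 2.3.1 names the liver as the target organ, and liver tests must be normal at entry.
- **The vital-sign part is weaker.** Criterion 4, Note 1 extends the Grade 1 exception to laboratory values only; SAP 9.7 assumes one for supine vital signs as well.
- **Replacing raw grades would mislead in its own way.** With raw grades at baseline and only worsened grades afterwards, a stable Grade 1 would look like recovery.

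These points limit the scope and decide the form of the remedy. None of them lets a by-arm table of graded results show who worsened.

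**Conclusion.** The point holds for the graded-result displays. Tables 33–37 ignore the participant's own baseline grade, so stable Grade 1 values accepted at entry reappear as Mild, and these tables cannot separate new grades from old ones. It does not extend to the adverse-event tables, the Grade 3 tolerability counts, or the tests that must be normal at entry.

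Its size depends on an assumed prevalence and on stable grades. For 10–40%, a difference of 25 points or more in either direction has probability 30–54% at 8:4. At 16 participants, over the splits tried, it is about 9–21% at 10% prevalence and 33–47% at 40%. It would be tempting to read 30–54% as the chance of a false signal against the drug. The documents do not support that: the figure is two-sided (the active-excess part is 12–27% at 8:4), the final Safety Population may exceed 12, and the baseline column or row would show the same imbalance. The trial tests no hypotheses, so what is at stake is the reading of descriptive tables.

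**What to change.** Keep the raw grades in Tables 33–37. For each parameter and direction, and for the Any parameter rows, add by arm one of the following:

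- a worsened-from-baseline maximum-grade count, including a participant only if the post-baseline grade exceeds their own baseline grade, with baseline as defined in SAP 3.1; or
- a shift table of baseline grade against maximum post-baseline grade.

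Add to the Table 37 note the sentence that already stands under Table 33, adapted to vital signs, saying that a graded result is an adverse event only if it worsened from baseline.

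The data are already collected. The cost is SAP shell wording, minor programming and slightly longer tables.

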#### 14.3.5.2 Hematology Results

##### Table 34: Hematology Laboratory Results by Parameter, Maximum Severity, Time Point, and Treatment Group, Safety Population

[Implementation Note: This table will be a similar format to [Table 33](#).

Parameters will be shown in the following order: Any Hematology Parameter, Hemoglobin, Platelets, White Blood Cells, Neutrophils, Lymphocytes, Monocytes, Basophils, and Eosinophils.

The following parameters may decrease: Hemoglobin, Platelets, White Blood Cells, Neutrophils, and Lymphocytes.

The following parameters may increase: Hemoglobin, White Blood Cells, Monocytes, Basophils, and Eosinophils.]

#### 14.3.5.2 Coagulation Results

**Table 35: Coagulation Laboratory Results by Parameter, Maximum Severity, Time Point, and Treatment Group, Safety Population**

[Implementation Note: This table will be a similar format to [Table 33](#).

Parameters will be shown in the following order: Any Coagulation Parameter, Prothrombin Time, and Activated Partial Thromboplastin Time (aPTT).]

#### 14.3.5.3 Urinalysis Results

##### Table 36: Urinalysis Laboratory Results by Parameter, Maximum Severity, Time Point, and Treatment Group, Safety Population

[Implementation Note: This table will be a similar format to [Table 33](#). Urinalysis will be presented for Days -1 (baseline), 4, and 8 and for each treatment group. Headers will not be split into Low and High, e.g., “Mild/Grade 1”.

Parameters will be shown in the following order: Any Urinalysis Parameter, Bilirubin, Nitrite, Urine Protein, Urine Glucose, White Blood Cell Count, Red Blood Cell Count, and Bacteria.

Urine microscopy parameters (WBC Count, RBC Count, and Bacteria) were only collected conditionally and thus will only be included if at least 5 participants reported a graded event. Otherwise refer to [Table 32](#).]

### 14.3.6 Displays of Vital Signs

**Table 37: Supine Vital Signs by Assessment, Maximum Severity, Time Point, and Treatment Group, Safety Population**

**[Implementation Note:** Vital signs will be presented for Days 1 (pre-dose 1)(baseline) through Day 9 for each treatment group. Dosing days (Days 1 through 7) will be separated by pre- and post- Morning and Evening dose. Follow-up assessments and Maximum Post Baseline will be Any Time.

If there are no life-threatening/grade 4 vital signs reported, then the columns will be omitted. If there is not at least one graded event for a treatment group within a parameter, then only “Max Severity Post Baseline” will be shown. If there are more than one graded event within a parameter for a specified time point, then report the maximum severity.

For grading not applicable to the specified parameter, then populate the cell with “N/A”. Otherwise, if the grade is zero counts, then populate the cell with “-”. Assessments will be shown in the following order: Any Vital Sign Assessment, Oral Temperature, Systolic Blood Pressure, Diastolic Blood Pressure, Pulse, and Respiratory Rate.

Assessments will specify low or high. If an assessment can be both high and low, then the low assessment will be listed first.

The following assessments may be low: Systolic Blood Pressure, Diastolic Blood Pressure, and Pulse.

All assessments may be high.]

Time Point	Dose	Treatment Group	N	None		Mild/ Grade 1		Moderate/ Grade 2		Severe/ Grade 3		Life-Threatening/ Grade 4	
				n	%	n	%	n	%	n	%	n	%
Any Vital Sign Assessment													
Day 1	Pre-Morning (Baseline)	400 mg SLV213	x	x	xx	x	xx	x	xx	x	xx	x	xx
		Placebo											
		All Participants											
	Post-Morning	400 mg SLV213											
		...											
	Pre-Evening	400 mg SLV213											
		...											
	Post-Evening	400 mg SLV213											
		...											

**Table 37: Supine Vital Signs by Assessment, Maximum Severity, Time Point, and Treatment Group, Safety Population (continued)**

Time Point	Dose	Treatment Group	N	None		Mild/ Grade 1		Moderate/ Grade 2		Severe/ Grade 3		Life-Threatening/ Grade 4	
				n	%	n	%	n	%	n	%	n	%
Day 2	Pre-Morning	400 mg SLV213											
		...											
	Post-Morning	400 mg SLV213											
		...											
	Pre-Evening	400 mg SLV213											
		...											
	Post-Evening	400 mg SLV213											
		...											
...	...	...											
Day 8	N/A	400 mg SLV213											
		...											
Day 9	N/A	400 mg SLV213											
		...											
Max Severity Post Baseline	Any Time	400 mg SLV213											
		...											
Oral Temperature													
Day 1	Pre-Morning (Baseline)	400 mg SLV213		x	x	xx	x	xx	x	xx	x	xx	x
	...	...											
Day 9	N/A	400 mg SLV213											
		...											

**Table 37: Supine Vital Signs by Assessment, Maximum Severity, Time Point, and Treatment Group, Safety Population (continued)**

Time Point	Dose	Treatment Group	N	None		Mild/ Grade 1		Moderate/ Grade 2		Severe/ Grade 3		Life-Threatening/ Grade 4	
				n	%	n	%	n	%	n	%	n	%
Max Severity Post Baseline	Any Time	400 mg SLV213											
		...											
Systolic Blood Pressure, Low													
Day 1	Pre-Morning (Baseline)	400 mg SLV213	x	x	xx	x	xx	x	xx	x	xx	x	xx
	...	...											
Day 9	N/A	400 mg SLV213											
		...											
Max Severity Post Baseline	Any Time	400 mg SLV213											
		...											
[Repeat for all vital sign assessments]													
Note: The “Max Severity Post Baseline” rows indicate the maximum severity experienced by each participant at any time point post baseline, including unscheduled assessments.													
N = Number of participants in the Safety Population with the laboratory result assessed at the respective time point; n = Number of participants with the maximum grade experienced for the specified assessment and time point.													
Vital signs were collected prior to and after each dose (morning and evening) on Days 1 through Day 9 and collected in the morning during follow-up visits (Day 8 and Day 9).													

